#### **4.11. Randomization and Blinding**

There will be no blinding or randomization.

## 5. DESCRIPTION OF PROCEDURES

A Schedule of Events is provided in [Appendix C](#), and the blood and urine sampling schedule in [Appendix D](#).

### 5.1. Medical Information

A medical history, weight, height, vital signs, and physical exam will be conducted after admission to the NIH CC and enrollment into the study. For subjects who are co-enrolled on the Natural History protocol 11-HG-0218, data collected for the Natural History study may be used in the screening/baseline phase if collected within 30 days prior to dosing Day 1.

Physical examinations will be standardized and performed by a credentialed nurse practitioner or physician who is an investigator in this protocol. This will document baseline status and ensure that the subject's medical health is adequate to undergo the proposed research procedures.

Subjects will undergo clinical evaluations while admitted by CC nursing staff or a member of the study team. Vital signs will be performed according to the unit schedule while inpatient and at least daily while outpatient. Medical evaluations and vital signs will be performed at other times if clinically indicated, or if the ongoing review of the data suggests a more detailed assessment of the vital signs is warranted.

All medical information, including physical examination, AEs, compliance with study procedures, concomitant medications, and other issues will be recorded during the treatment phase on CRFs by the study team.

### 5.2. Diagnostic Studies

During the interventional phase, blood and urine will be collected for safety, PK, and PD evaluations. Safety will also be assessed by AEs, physical examinations, vital signs, and clinical laboratory tests. No radiation or sedation will be used as part of this study unless clinically indicated. Other diagnostic studies may be performed, if clinically indicated.

#### 5.2.1. Procedures

##### 5.2.1.1. Muscle Biopsy

Muscle biopsies will be performed for research purposes. Muscle biopsies will only be performed at the baseline and 91 day (3-month) visits; therefore a maximum of 4 incisions will be done per patient. Muscles to be biopsied include 1) the biceps brachii in the upper extremity and 2) a lower extremity muscle that has been determined as suitable for biopsy by MRI. Two biopsy sites are necessary to have a homogenous sampling from all subjects (through the biceps brachii, a muscle that is easily accessible and only affected in the advanced stage of the disease), and to further test if ManNAc supplementation could reverse the STIR-bright areas that are consistently seen in GNE myopathy subjects. Both upper (biceps brachii) and lower extremity muscle biopsies will be performed at the same time to decrease the subject's discomfort. Repeat MRI at 91 days (3 months) will guide the selection of the muscle to be biopsied for the 91 day (3-month) visit (see Section 5.2.1.1.1). A total of four muscle biopsies will be performed for each subject: two biopsies at baseline and two biopsies at 91 days (3 months).

### 5.2.1.1.1. Selection of Muscle Biopsy Site

The selection of muscles to be biopsied will be performed by identifying the following characteristics on muscle MRI: 1) Minimal or no fatty replacement and 2) Presence of hyperintense short tau inversion recovery (STIR). Fatty tissue is not informative and STIR hyperintensity is a signal of disease activity. Whenever possible, we will avoid performing biopsies of the quadriceps muscle, as disease characteristics are not likely to be significant in this muscle group. An MRI will be repeated before the 91 day (3-month) muscle biopsy to identify the area for biopsy; if feasible, the 91 day (3-month) biopsy will be the contralateral muscle biopsied at baseline.

### 5.2.1.1.2. Method for obtaining muscle biopsy

Muscle will be obtained by open muscle biopsy. This procedure is used because it allows safe access to muscles while carefully avoiding local blood vessels and nerves.

[figure not shown]
An open-muscle biopsy is a minor surgical procedure performed by a qualified neurologist or neurosurgeon with expertise in this technique. It is performed in the operating room under local anesthesia. After the skin is cleaned and draped, the skin will be infiltrated with local anesthetic which may cause mild discomfort. After a small (approximately 1.5 inches long) skin incision, the desired tissue (muscle) is isolated and biopsied. Two clamped muscles samples, each no greater than 0.5 inches (longitudinal axis) X 0.25 inches (cross-sectional diameter), will be obtained from each biopsy site. The incision site will be closed by a method according to the surgeon's preference.

The biopsy samples will be placed on sterile, saline-dampened gauze and will be processed immediately after collection.

### 5.2.1.2. Muscle Magnetic Resonance Imaging and Spectroscopy (MRI/MRS)

Muscle MRI/MRS will be performed at baseline, 91 days (3 months) and 365 days (12 months) in lower extremity muscles to monitor areas of disease activity. Findings are characterized by T2-weighted STIR hyperintensity of muscles actively affected, followed by fatty-fibrous replacement on T1-weighted imaging. MRS will noninvasively monitor muscle metabolism and degree of involvement (Figure 7).

**Figure 7. MRS of GNE Myopathy Muscle**

### 5.2.1.3. Quantitative Muscle Strength Assessment (QMA)

Muscle strength will be evaluated at baseline and at every follow-up visit utilizing the Quantitative Muscle Strength Assessment (QMA) which measures maximal voluntary isometric contraction (MVIC) in kilograms (kg) using a fixed frame dynamometer, a strain gauge tensiometer, and a computer-aided acquisition system (Aeverl Medical, Gainesville GA, USA) to measure maximal strength in 13 muscles groups. The muscle strength in kg is compared to predicted strength for age, gender, height and weight to generate a proportion of predicted strength value.

### 5.2.1.4. Other Rehabilitation Medicine Assessments

Other assessments may be performed at baseline and follow-up visits and will include muscle strength using the 10-point manual muscle testing (MMT-28) scale, Adult Myopathy Assessment Tool (AMAT), 6-min walk test (may be replaced by 10-meter walk test), timed up-and-go test, forward/functional reach test. The Jebsen Standardized Hand Function test will be done at baseline, 365 days (12 months) and 730 days (24 months).

### 5.2.1.5. Activity Monitor

Changes in daily activity will be measured using a Fitbit One™ activity monitor (Fitbit Inc., San Francisco, CA) in ambulatory subjects who also possess a compatible home computer. Recent studies have demonstrated that consumer-grade activity monitors reliably measure activity (steps taken, stairs climbed, and distance walked) in persons with disabilities when compared to the Step Activity Monitor, which has been validated in various disabled populations for more than a decade. The Fitbit will allow measurement of activity at a substantially reduced cost. Subjects will wear the device on a waistband, in a pocket, or with a necklace or wristband. They will use the monitor throughout the study. The subjects will register the device's software on their home computer in an anonymized fashion. They will use a study identifier for their name and will not use their own home address. Anonymized e-mail addresses will be created for subjects by the research team. Subjects' activity (walking, steps taken, distance walked) will be automatically uploaded to the anonymous profile. Fitbit data from each subject will be migrated to the study's database (Fitbase) for future analysis.

### 5.2.1.6. Patient-Reported Outcomes

Patient-Reported Outcomes will be collected at the time of study enrollment (baseline) and at each return visit unless otherwise indicated in the Table below. These will include the Human Activity Profile (HAP), the Inclusion Body Myositis Functional Rating Scale (IBMFRS), the Activity Balance Confidence (ABC) Scale, the Patient-Reported Outcomes Measurement Information System (PROMIS) questionnaires, Global Rate of Change questionnaire, AMAT Anchor, and Functional Questionnaire.

Questionnaire	Concept	Burden
Human Activity Profile (HAP)	Energy expenditure/ physical fitness	94 items/ 5-7 minutes
Inclusion Body Myositis Functional Rating Scale	Function specific	10 item/ <5 minutes
Activity Balance Confidence	Risk for falls	10 items <5 minutes

Global Rate of Change	Assess patient-reported changes between start of trial and follow-up visits	4 items/ <5 minutes Only at follow-up visits
PROMIS questionnaire	Emotional and psychosocial well-being, and fatigue and sleep	32 items/ ~10 minutes
AMAT Anchor	Patient-reported outcome for muscle strength measure validation	6 items/ <5 minutes Only visit Day 85
Functional Questionnaire	Assess device use, employment status, disability status	4 items/ <5 minutes Only at baseline

### 5.2.2. Clinical Laboratory Studies

Clinical laboratory samples will be collected at pre-dose (baseline) and for safety evaluations on Days 2, 5, 8, and 10 ( $\pm 1$ ) and at 456 (15 months), 638 (21 months) and 820 (27 months) days (at the NIH clinical center or subjects' home lab or physician) and at every follow-up visit (see [Appendix D](#)). For subjects who are co-enrolled on the Natural History protocol 11-HG-0218 and combine a natural history visit with this study, clinical laboratory tests collected for the Natural History study may be used as the pre-dose evaluation for this trial if within 30-days prior to initial dosing. Clinical laboratory tests will be evaluated and noted in a CRIS progress note. Laboratory results outside of CC normal parameters but not of clinical significance will be noted in the CRIS progress note.

#### 5.2.2.1. Hematology/Chemistry

Blood samples for the clinical laboratory tests will be collected by CC phlebotomy or nursing staff using either an indwelling peripheral catheter or by venipuncture. Testing will include the following:

- Hematology: complete blood count (CBC) with differential, platelet count, reticulocyte count and erythrocyte sedimentation rate (ESR), C-reactive protein, prothrombin time (PT), and partial thromboplastin time (PTT).
- Serum chemistry: acute care panel (sodium, potassium, chloride, carbon dioxide, glucose, creatinine, blood urea nitrogen (BUN)), mineral panel (albumin, calcium, magnesium, phosphorus), hepatic panel (alkaline phosphatase, alanine aminotransferase (ALT), aspartate aminotransferase (AST), direct bilirubin), lipid panel, creatine kinase, c-reactive protein, and cystatin-C.

#### 5.2.2.2. Pregnancy Testing

A urine human chorionic gonadotropin (hCG) test will be required at screening/baseline in female subjects with childbearing potential and be repeated within 7 days prior to starting administration of study drug. Subjects will not be eligible for the study if the pregnancy test is positive. Urine hCG will be repeated at every follow-up visit.

#### 5.2.2.3. Urinalysis

Urinalysis will assess urine protein, glucose, ketones, hemoglobin, urobilinogen, leukocyte esterase, nitrite, red blood cells (RBC's) and WBC's.

### 5.2.3. Pharmacokinetics

Plasma concentrations of ManNAc and free Neu5Ac will be quantified using validated LC-MS/MS methods ([name] *et al.*, unpublished data). The method has been validated thoroughly to support clinical trials and has a calibration range of 10 to 5000 ng/mL.

We will administer multiple doses of ManNAc to achieve steady state. Plasma concentrations of ManNAc and free Neu5Ac will be measured at 0 (pre-dose), 0.5, 1, 2, 3, 4, 6, 8, 10 and 12 hours after the first study drug administration (Day 1). On Day 2-7, and 45 ( $\pm 7$ ), morning  $C_{\text{trough}}$  (i.e., immediately before administering the morning dose of the study drug) measurements will be performed.  $C_{\text{trough}}$  will be collected pre-dose on Days 180, 365 and prior to the final dose of study drug. (See [Appendix D](#) for time points).

At the 30 month visit, plasma samples for ManNAc and Neu5Ac PK under TID dosing will be collected at 0 (pre-dose), 2, 4, 6, 8, 24 and 48 hours after the first study drug administration on TID dosing. Plasma will be collected right before ManNAc dose (trough) at the 8, 24 and 48 hour timepoints. Patient will avoid ingestion of ManNAc for 5-7 days prior to pre-dose PK draw on TID dosing.

The primary PK parameters that will be assessed for both plasma ManNAc and free Neu5Ac include:

- Maximum observed plasma concentration ( $C_{\text{max}}$ ),
- Time to  $C_{\text{max}}$  ( $T_{\text{max}}$ ),
- Area under the plasma concentration-time curve from time 0 to infinity ( $AUC_{0-\infty}$ ),
- Area under the plasma concentration-time curve from time 0 to time of last measurable plasma concentration ( $AUC_{\text{last}}$ ),
- Area under the plasma concentration-time curve within the dosing interval ( $AUC_t$ ),
- Plasma elimination half-life ( $t_{1/2}$ ).

A pre-dose sample may be evaluated to investigate allelic variants of drug metabolism enzymes, if variable PK data are encountered in subjects.

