**Table 1. PK and PD Parameters for Single Dose of Oral ManNAc to Fasting GNE Myopathy Subjects**

Dose (mg)	$T_{max}$  (hr)	$C_{max}$  (ng/mL)	$C_{max}$ Ratio		Mean AUC 0-∞ (ng*hr/mL)	AUC Ratio	
			Dose Compared	Ratio		Dose Compared	Ratio
Plasma ManNAc							
3,000	2	1,451	6,000 mg/3,000 mg	0.9	8,244	6,000/ 3,000 mg	1.2
6,000	2.5	1,336	10,000 mg/6,000 mg	1.9	9,552	10,000/6,000 mg	1.5
10,000	2	2,585	10,000 mg/3,000 mg	1.8	14,161	10,000/3,000 mg	1.7
Plasma Free Neu5Ac							
3,000	10	115	6,000 mg/3,000 mg	1.6	2147	6,000/ 3,000 mg	1.9
6,000	11	181	10,000 mg/6,000 mg	0.8	4171	10,000/6,000 mg	0.7
10,000	8	143	10,000 mg/3,000 mg	1.2	3007	10,000/3,000 mg	1.4

Median;  Geometric Mean PK calculations were conducted with baseline adjustment by subtracting ManNAc or Neu5Ac concentrations at  $t=0$  for each subject.

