#### 4.5.3. Drug Administration During Terminal Half-Life PK Determination

Terminal half-life will be determined during the Day 85 visit. While the subject is inpatient, the study drug will be withheld for 72 hours with the purpose of determining terminal half-life PK parameters.

Day 85			
Midnight-0 0: 0800: 0800-0900: 0900:	Water only Terminal half-life DOSE Water only May resume regular diet		

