## 6. DESCRIPTION OF STUDY POPULATION

### 6.1. Estimated Number of Participants

This study will enroll 12 subjects with GNE myopathy divided into two dosing cohorts (cohort size = 6) assigned to receive ManNAc at either 3,000 mg BID or 6,000 mg BID for a 7-day pharmacokinetics study, for a total of 6,000 mg or 12,000 mg per day, respectively. All patients receive 6,000 mg BID for the remainder of the study beyond 7 days. Accrual ceiling will be set at 30 subjects to allow for subject replacement if needed. We anticipate enrollment of the 12 subjects within 1 year.

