#### **7.2.4. Pharmacodynamics**

Different dose levels will be evaluated by a statistical dose-response model of the relationship between dose and the rate at which plasma free Neu5Ac returns to baseline levels.

The following PD parameters may be summarized and analyzed by treatment group: Intracellular ManNAc, Neu5Ac, CMP-Neu5Ac and plasma sialylation (may include T/ST ratios). A similar statistical dose-response model may be used to evaluate these parameters, if appropriate.

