**APPENDIX D. BLOOD/URINE SAMPLING SCHEDULE****Baseline and Pharmacokinetic Phase**

Sample	Timepoints																						Sample	Blood Volume (mL)	Lab		
	Baseline	PK Phase																				Safety Phase					
		Day 1 (hours post-dose)										Day 2-6	Day 7 (hours after last dose)													Day 8-10	
		Pre 	0.5	1	2	3	4	6	8	10	12 	Pre 	Pre 	0.5	1	2	3	4	6	8	10	12					
Blood PK 	X	X	X	X	X	X	X	X	X	X	X	X	X	X	X	X	X	X	X	X	X	X		Blood	3	Alliance	
Clinical labs 	X											X	X											X	Blood/ Urine	14.5	NIH DLM
PD 	X							X		X	X	X	X											X	Blood	20	Alliance
Research labs 	X											X	X											X	Blood/ Urine	10-30	[name]/ TRND
Urine PK 		X		X		X		X			X	X	X														

Blood for plasma PK analysis will be collected on Day 1 at pre-dose and at 0.5, 1, 2, 3, 4, 6, 8, 10, 12 hours after the first administration of study drug. Note that 12-hour timepoint should be collected immediately before administering the evening dose of study drug (trough level).

On Days 2-6 (weekdays only), samples will be collected immediately before administering the morning dose of the study drug.

On Day 7, blood will be collected before the morning dose and at 0.5, 1, 2, 3, 4, 6, 8, 10 and 12 hours after morning administration of study drug. Note that 12-hour timepoint should be collected immediately before administering the evening dose of study drug (trough level) (Section 5.2.3)

Collection of trough blood samples (immediately before drug administration).

Clinical laboratory test will be collected to perform safety evaluation at baseline, on Day 2, 5 and 8 ( $\pm 1$ ). Subjects in Cohort A will have an additional test on Day 10 ( $\pm 1$ ). Clinical laboratory tests will include CBC with differential, platelet count, reticulocyte count, ESR, C-reactive protein, PT, and PTT, acute care panel (sodium, potassium, chloride, carbon dioxide, glucose, creatinine, blood urea nitrogen (BUN)), mineral panel (albumin, calcium, magnesium, phosphorus), hepatic panel (alkaline phosphatase, alanine aminotransferase (ALT), aspartate aminotransferase (AST), direct bilirubin), GGT, lipid panel, creatine kinase, and cystatin-C, urinalysis, and pregnancy test (Section 5.2.2)

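### The Section 7.2.4 dose model needs a Neu5Ac return-to-baseline curve at each dose, but the planned sampling gives one at 6,000 mg BID only; Neu5Ac AUC0-inf and half-life at 3,000 mg BID fail for the same reason

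*Combined protocol and SAP*

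**What the plan says.** **Parameters.** Section 5.2.3 introduces its list with "The primary PK parameters that will be assessed for both plasma ManNAc and free Neu5Ac include". The list includes AUC0-inf and half-life and names no study days. Section 7.1.1 plans summaries by treatment group, 6,000 and 12,000 mg per day (3,000 and 6,000 mg BID). Section 7.2.3 uses noncompartmental methods.

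**Dose model.** Section 7.2.4 says dose levels will be evaluated with a statistical model of "the relationship between dose and the rate at which plasma free Neu5Ac returns to baseline levels".

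**Sampling on Days 1 and 7.** Section 5.2.3 ends the Day 1 series at "10 and 12 hours after the first study drug administration (Day 1"). Appendix D repeats this a week later: "On Day 7, blood will be collected before the morning dose and at 0.5, 1, 2, 3, 4, 6, 8, 10 and 12 hours". On both days the "12-hour timepoint should be collected immediately before administering the evening dose of study drug (trough level"). Appendix D marks no blood PK sample on Days 8-10, and Table 7 gives no PK volume on Day 9.

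**Later profiles.** Section 4.5.3 states: "Terminal half-life will be determined during the Day 85 visit". Drug is then withheld and Appendix D samples to 72 h. By that time, under Section 6.1, "All patients receive 6,000 mg BID for the remainder of the study beyond 7 days". The 30-month profile is at 4,000 mg TID with dosing continuing through the sampling.

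**The concern.** A return-to-baseline rate can only be measured after the peak, with the next dose withheld. Neu5Ac peaks late: Table 1 puts the median Tmax at 10 h after 3,000 mg and 11 h after 6,000 mg. A 12 h profile closed by the next dose therefore sees almost none of the decline, and 3,000 mg BID has no other planned serial profile.

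The protocol's own background expects the rate to differ by dose. Section 4.4.2 says Neu5Ac is back to baseline by 24 h after a single 3,000 mg dose but still above it at 48 h after 6,000 mg. Section 7.2.4 is meant to examine that contrast, and the schedule supplies one side of it. If the text stands, the dose-response analysis has one dose level. A by-group table of Neu5Ac AUC0-inf and half-life would hold either blanks or extrapolations from one or two points near the peak.

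**Working it through.** **1. Inputs.** Table 1, free Neu5Ac, single dose, baseline-adjusted:

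| Dose | Median Tmax | Geometric mean Cmax | Mean AUC0-inf |
|---|---|---|---|
| 3,000 mg | 10 h | 115 ng/mL | 2,147 ng·h/mL |
| 6,000 mg | 11 h | 181 ng/mL | 4,171 ng·h/mL |

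**2. Reproducing the plan's figures.** The 6,000/3,000 mg ratios are 181/115 = 1.57 (stated 1.6) for Cmax and 4,171/2,147 = 1.94 (stated 1.9) for AUC. Table 7 confirms the sampling lengths. Ten samples × 3 mL = 30 mL on Days 1 and 7. Thirteen samples × 3 mL = 39 mL = 30 + 3 + 3 + 3 on Days 90-93.

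**3. Samples after the median peak.** In the 12 h profile only the 12 h sample falls after 10 h or 11 h, so there is one sample at either dose and no terminal slope can be fitted. The 72 h profile has four: 12, 24, 48 and 72 h.

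**4. AUC beyond 12 h.** Concentration never exceeds Cmax, so AUC0-12 ≤ 12 × Cmax, and the share beyond 12 h is at least 1 − 12 × Cmax / AUC0-inf.
- 3,000 mg: 1 − 12 × 115/2,147 = 1 − 1,380/2,147 = 36%.
- 6,000 mg: 1 − 12 × 181/4,171 = 1 − 2,172/4,171 = 48%.

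These figures are approximate because Table 1 pairs a geometric mean Cmax with a mean AUC of unstated type. Suppose the AUC is an arithmetic mean of log-normal data with a CV of 30-60% (assumption). Its geometric mean is then AUC/√(1 + CV²), that is AUC/1.044 to AUC/1.166. The shares become:
- 3,000 mg: 1 − 1,380/2,056 = 33% down to 1 − 1,380/1,841 = 25%.
- 6,000 mg: 1 − 2,172/3,995 = 46% down to 1 − 2,172/3,577 = 39%.

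The real shares should be larger, since concentration is below Cmax for most of the 12 h.

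**5. Illustration with an assumed shape.** Take a curve proportional to t^a × exp(−bt), matched to Tmax and to AUC/Cmax (18.7 h and 23.0 h). It puts about 57% (3,000 mg) and 65% (6,000 mg) of AUC beyond 12 h. At 3,000 mg the 10-12 h slope gives an apparent half-life of 40 h, against 5 h for the same curve over 24-48 h. At 6,000 mg there is no decline between 10 and 12 h. A half-life computed from such data would be an artefact.

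**6. ManNAc.** The median Tmax is 2-2.5 h at these doses, so six samples follow it. With a half-life of about 2.4 h, 12 h is 5 half-lives, and 0.5^((12 − 2)/2.4) = 6% of the 2 h level remains at 12 h. ManNAc AUC0-inf and half-life are estimable from the 12 h profiles.

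**The case against.** The other side has several good points.

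- No text assigns Neu5Ac AUC0-inf to Days 1 and 7, and Section 4.5.3 already places half-life at the Day 85 visit. Section 7.2.3 uses permissive wording and names only Cmax and interval AUC for its early-day comparison. This stands, and much of the fix agrees with it. But Section 5.2.3 commits to the parameters without tying them to days, and Section 7.2.4 commits firmly to the dose model.
- A reader might infer that a primary objective requires these results by dose. Section 2.1 does not say so. The by-group requirement comes only from the general convention in Section 7.1.1.
- A reader might infer that no 3,000 mg BID profile could ever run longer. Section 4.4.1 and Table 6 allow reduced doses, including 3,000 mg BID, so a de-escalated subject could have a 72 h profile on it. That would be an unplanned, selected subset, not the planned comparison.
- A reader might infer that the values cannot be obtained by any method. The population model in Section 3.8.4 covers both analytes and might supply them, and Table 1 already gives a single-dose 3,000 mg AUC0-inf. Section 7 does not specify that model for this use, so the limit is on the planned noncompartmental analysis.
- A reader might expect same-day pre-dose subtraction on Day 7 or Day 85, which would remove drug-derived Neu5Ac. The Table 1 note, "PK calculations were conducted with baseline adjustment by subtracting ManNAc or Neu5Ac concentrations", describes the Phase 1 calculation. Nothing in Sections 5.2.3 or 7.2.3 extends it to those days.
- Section 7.1.1 describes tests and intervals as interpretive aids, not claims. That lowers the stakes but does not make the dose model fittable.

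**Conclusion.** The concern holds for Neu5Ac. As planned, only 6,000 mg BID has a return-to-baseline curve, so the Section 7.2.4 model relating dose to return rate cannot be fitted as written. Nor can noncompartmental analysis give Neu5Ac AUC0-inf or half-life at 3,000 mg BID, or at either dose from a 12 h profile. Roughly 36% (3,000 mg) and 48% (6,000 mg) or more of AUC0-inf lies beyond 12 h, or about 25-33% and 39-46% under the assumed CVs; the conclusion is the same across that range. It rests on the Phase 1 single-dose medians in Table 1, since individual Tmax values are not given, and on subjects following the planned dose.

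It does not extend to ManNAc, to Neu5Ac half-life at 6,000 mg BID, or to Neu5Ac Cmax, Ctrough and 12 h interval AUC, all of which remain available.

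**What to change.** - **Section 7.2.4:** base the 3,000 v 6,000 mg BID comparison on Day 1 and Day 7 Neu5Ac exposure (AUC over the dosing interval, Cmax, Ctrough) instead of the rate of return to baseline.
- **Sections 5.2.3 and 7.2.3:** state that Neu5Ac AUC0-inf and half-life are not reported from the 12 h profiles. Report Neu5Ac half-life only from the Day 85-90 profile, labelled with the dose each subject is actually taking (planned 6,000 mg BID). Section 7.2.3 compares Day 1 with Day 8, a day with no scheduled profile; reconcile that in the same edit.

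**Cost.** The by-dose return rate and by-dose Neu5Ac AUC0-inf and half-life are no longer reported. The change replaces a pharmacodynamic measure and alters protocol as well as analysis wording, so it should be made before database lock. No sampling is added.

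**Caveat on the retained half-life.** Table 4 simulates average Neu5Ac at 6,000 mg BID rising from 219 (Day 1) to 826 ng/mL (Day 30). Assume one compartment, with Day 30 at steady state, and solve 1 − (1 − e^(−x))/x = 1/R for x = 24 × ln 2 / half-life. R = 826/219 = 3.77 gives about 26 h. Subtracting a 150 ng/mL baseline, R = 676/69 = 9.80 gives about 76 h. On those values 72 h spans only about 1-3 half-lives, so the report should state how much of the decline was observed.
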